Merck Investigator Studies Program (MISP)

IIS Protocol Template

Requirements for Submitting a Full Proposal

[figure not shown]
Section #1 - MISP Protocol Identification

Study Title:	A double-blind, randomized and controlled multicenter prospective trial to compare the oncological benefit of deep neuromuscular block in gastric cancer obesity patient
Request Date:	3rd August 2016
Last update date:	8th May 2020
Institution Name	Korea University College of Medicine
Investigator Contact Information: - Full address - Phone No. - Fax No. - E-mail	[name] Addr, Department of Surgery, [name] Tel, [name] Fax, [name] Email, [contact]

Registered in www.clinicaltrials.gov as NCT03196791

Section #2- Core Protocol	
2.1 Objectives & Hypotheses	
2.1 List the objectives.
 
The present randomized study is designed to evaluate the impact of muscle relaxation during laparoscopic gastrectomy on oncological benefit, especially with obese patients over BMI 25. Because surgeons still find that laparoscopic surgery for obese patients is challenging. The retrieval of lymph nodes (LNs) is difficult because they are embedded in thick fat tissue and are hard to distinguish with surrounding fat so that, the operative time should be prolonged. Studies have revealed that the association between obesity and longer operative outcomes than normal body weight patients. Therefore we assumed deep neuromuscular block was associated more adequate lymphadenectomy, smaller intraoperative bleeding, shorter operative time.
 
2.1.1 List the clinical hypotheses.
 
The primary endpoint is number of harvested lymph node that is critical point regarding quality of surgery in gastric cancer treatment. The secondary endpoint is intraoperative bleeding, surgeons' satisfaction.

2.2 Background & Rationale, Significance of Selected Topic & Preliminary Data	Administration of muscle relaxation is essential in a variety of procedures as it causes an improvement of surgical conditions. Until recently, intraoperative deep neuromuscular block was eschewed because of concerns about recovery at the end of surgery. Since 2009, many studies have confirmed the rapid efficacy and better safety of sugammadex for reversing moderate and deep neuromuscular blockades induced by steroid muscle relaxants than standard reversing agents, but most of studies have been focused only on surgical condition or concerns from the view points from anesthesiologists.
2.3 Study Design	Prospective, Randomized, double blind controlled trial Multicenter trial : 9 centers

2.4 Study Flowchart

2.5 Study Procedures	
Inclusion criteria
 
 1. Patient with obtaining written informed consent 2. American Society of Anesthesiologists Physical status I or III, Aged 19 to 75 yr 3. Underwent elective laparoscopic distal gastrectomy 4. Body mass index (BMI) > 25 kg/m² 5. CStage I, II 
Exclusion criteria
 
 1. End stage renal disease (ESRD) patient 2. A (family) history of malignant hyperthermia; significant renal or hepatic dysfunction; known or suspected neuromuscular disorders; allergies to narcotics or muscle relaxants; known previous abdominal surgeries 
Anesthetic protocol
 
 1. The patients were randomly assigned to two groups using a computer-generated randomization table: 
 1) Deep neuromuscular block group the 'post-tetanic counts 1-2' (PTC1-2) 2) Moderate neuromuscular group the 'train-of-four counts 1-2' (TOF count1-2) 2. Premedication : None 3. Standard monitoring included electrocardiogram, noninvasive blood pressure and pulse oximetry at OR 4. Anesthesia is induced and maintained with propofol and remifentanil (BP within \pm 20% of preinduction values) 
 – TIVA TCI (target controlled infusion using effect-site concentration) 5. After loss of consciousness is confirmed, neuromuscular activity monitoring via acceleromyography is initiated. 
 -Neuromuscular monitoring was performed using a TOF-Watch SX® (Organon; Roseland, NJ, USA) at the adductor pollicis muscle. -The ulnar nerve was supramaximally stimulated near the wrist with square pulses of 0.2 ms duration, delivered as TOF pulses of 2 Hz at 15-second intervals. The resulting contractions of the adductor pollicis muscle were quantified using an acceleromyographic monitor. -The acceleromyograph was calibrated with 50 Hz tetanic stimulation for 5 s and train-of-four (TOF) stimulation for 3 min 6. Muscle relaxation is induced rocuronium bromide (0.6 mg/kg) 7. Mechanical ventilation was initiated. 
(Tidal volume : Ideal body weight (IBW) *8, Respiratory rate (RR) : EtCO₂ 35-45 유지)
 8. Hypnotic depth was kept in the range of 45 to 60 using BIS VISTA® (Aspect Medical Systems, Inc., Norwood, MA, USA). 
9. Neuromuscular blocking agent protocol
 
Neuromuscular assessment
 
Neuromuscular monitoring was performed using a TOF-Watch®. The ulnar nerve was supramaximally stimulated near the wrist with square pulses of 0.2 ms duration, delivered as TOF pulses of 2 Hz at 15-second intervals. The resulting contractions of the adductor pollicis muscle were quantified using an acceleromyographic monitor. TOF stimulation and PTCstimulation were repeated every 15 s and twomin, respectively.
 
In Moderate neuromuscular group

-----------------------------	--

	
If TOF count 1-2, rocuronium bromide 0.1-0.5 mg/kg/hr continuous infusion with TOF monitoring
 
In Deep neuromuscular group followed by a continuous infusion of 0.5–1.0 mg/kg/hr (IBW) with TOF monitoring
 
10. Additionally, if the surgeon asked the anesthesiologist for deeper NMB to achieve an adequate surgical field, rocuronium bolus 0.15 mg/kg was administered.
 
11. rocuronium infusion stop at end of Laparoscope
 
12. Reversal agent & Dose protocol
 
 -In Moderate neuromuscular group (second twitch appeared at TOF) Sugammadex 2mg/kg (Bridion®, (MSD)) -In Deep neuromuscular group (end of surgery) Sugammadex (Bridion®, Merck Sharp and Dohme (MSD), Oss, The Netherlands) 4 mg/kg 
13. When the TOF ratio recovered to 0.9 and spontaneous breath, opening of the eyes to verbal commands, extubation will be done.
 
14. Insufflation pressure: 12mmHg
 
Evaluation method
 
At OR : Anesthesiologists
 
 Total anesthesia time Total surgical time (Incision – dressing) The time from the end of the operation to the administration of the reversal agent Total fluid Total rocuronium dose Hemodynamic parameter systolic,diastolic,mean BP -HR -EtCO₂ -Temperature -Peak inspiration pressure 
Sedation score(MOAA/S)
 
  
 0	does not respond to pain	
 
 1	does not respond to mild prodding or shaking	
 
 2	responds only after mild prodding or shaking	
 
 3	responds only after name is called loudly and/or repeatedly	
 
 4	lethargic response to name spoken in normal tone	
 
 5	responds readily to name spoken in normal tone	
  
 
Surgeon
 
Report of surgeon's specific complaints
 
The wasting operative time due to poor neuromuscular relaxation
 
Patient motion
 
Surgical rating score : consists of individual 4 parts of critical lymph node dissection areas -
 
during lymph node dissection at 4sb, 6, supraduodenal area and suprapancreatic area
	0	does not respond to pain	1	does not respond to mild prodding or shaking	2	responds only after mild prodding or shaking	3	responds only after name is called loudly and/or repeatedly	4	lethargic response to name spoken in normal tone	5	responds readily to name spoken in normal tone
0	does not respond to pain												
1	does not respond to mild prodding or shaking												
2	responds only after mild prodding or shaking												
3	responds only after name is called loudly and/or repeatedly												
4	lethargic response to name spoken in normal tone												
5	responds readily to name spoken in normal tone												

	
1 Extremely poor conditions: the surgeon is unable to work because of coughing or because of the inability to obtain a visible laparoscopic field because of inadequate muscle relaxation. Additional neuromuscular blocking agents must be given
 
2 Poor conditions: there is a visible laparoscopic field, but the surgeon is severely hampered by inadequate muscle relaxation with continuous muscle contractions, movements, or both with the hazard of tissue damage. Additional neuromuscular blocking agents must be given
 
3 Acceptable conditions: there is a wide visible laparoscopic field but muscle contractions, movements, or both occur regularly causing some interference with the surgeon's work. There is the need for additional neuromuscular blocking agents to prevent deterioration
 
4 Good conditions: there is a wide laparoscopic working field with sporadic muscle contractions, movements, or both. There is no immediate need for additional neuromuscular blocking agents unless there is the fear of deterioration
 
5 Optimal conditions: there is a wide visible laparoscopic working field without any movement or contractions. There is no need for additional neuromuscular blocking agents
 
Ward Pain score using the VAS until postoperative 48 hours PONV Count of rescue medication First flatus time Postoperative complication until POD 30

2.6 Study Duration	2 years after IRB approval
2.7 Statistical Analysis and Sample Size Justification	
Statistical analyses were performed with IBM SPSS 20 software. Quantitative variables were expressed as means (standard deviation) and were compared by Mann-Whitney and Wilcoxon nonparametric tests. Qualitative variables were described by numbers and percentages and 95% confidence intervals. The various parameters were compared by Pearson' s and Fisher's Chi-squared tests. For all statistical tests, a P value < 0.05 was considered significant
 
The major objective of this study is to estimate the number dissected lymph nodes. Based upon a sample size of n=89 patients per group, this study has 80% power to detect a 6.3 difference between groups in harvested lymph nodes; this calculation is based on a between subject standard deviation of change of 15 for harvested lymph node (reference for where this variability statement originated). The calculations are the customary ones based on normal distributions –estimation of sample size and power for comparing two means in Bernard Rosner's fundamentals of biostatistics. After considering 10% of follow-up loss, a total of 196 patients will be needed.
 
Regarding increasing effect of BMI on surgery, we will process it as continuous variable when we analyze data and if there is significance, we could decide a cut off value of BMI for specific anesthetic indication.
 
In addition, to control the surgeons' factors impacting results, we will perform surgeon stratified randomization. And if there is a serious surgeon's technical problems being able to distort objective data when interim analysis, we would drop the surgeon out of this study.

2.8 Specific Drug Supply Requirements	
N/A

2.9 Adverse Experience Reporting	
Reporting Procedures for Exchange of Adverse Event Information.
 
(i) For purposes of this Agreement the below terms shall be defined as follows:
 
“Adverse Event” or “AE” shall mean any untoward medical occurrence in a Study subject who is administered the Study Drug regardless of whether or not a causal relationship with the Study Drug exists. By way of example and without limitation, an AE can be any unfavorable and unintended sign (for example, an abnormal laboratory finding), symptom, or disease temporally associated with the use of the Study Drug.
 
“Device Deficiency” shall mean inadequacy of a Study Drug device related to its identity, quality, durability, reliability, safety or performance, such as malfunction, misuse or use error and inadequate labeling.
 
“Incident” shall mean any malfunction or deterioration in the characteristics and/or performance of a Study Drug device, as well as any inadequacy in the labeling or the instructions for use which, directly or indirectly, might lead to or might have led to the death of a patient, or user, or of other persons or to a serious deterioration in the state of health.
 
“Medical Device Event” shall mean any malfunction or deterioration in the characteristics and/or the performance of a Study Drug device, as well as any inadequacy in the labeling or the instructions for use which led to or could have led to an untoward event for the user or any other person.
 
“Serious Adverse Event” or “SAE” shall mean any untoward medical occurrence in a Study subject who is administered the Study Drug that results in death, a life-threatening drug experience, requires inpatient hospitalization or prolongation of existing hospitalization, results in persistent or significant disability/incapacity, or is a congenital anomaly/birth defect, cancer, or is a new cancer if the cancer is the condition of the study, or overdose. Other important medical events that may jeopardize the patient or may require intervention to prevent one of the outcomes listed previously should also be considered “serious”.
 
“Suspected Unexpected Serious Adverse Reaction” or “SUSAR” shall mean any Serious Adverse Event, the nature, severity or frequency of which is not consistent with information in the most current investigator’s brochure, or with respect to a marketed product the most current Summary of Product Characteristics (SPC) or Package Insert.

	
(ii) Serious Adverse Event and Suspected Unexpected Serious Adverse Reaction, Medical Device Event, Potential Incident, Device Deficiency or Incident Reporting: Principal Investigator shall forward to MSD's Global Safety ("MSD GS") group, any SAE and SUSAR, Medical Device Event, Device Deficiency or Incident information, including, but not limited to, all initial and follow-up information involving any Study subject in the Study. Notification shall be in the form of a completed CIOMS I/MedWatch (or other mutually agreed upon format) within two (2) business days of learning of the information. This information shall be transmitted to MSD GS using the contact information provided below or such other modified contact information as provided by MSD in writing. All information shall be transmitted in the English language and contain the reporter's name and the Study subject identifier code. SUSAR information will be reported unblinded if the Study Drug has been blinded in the Study. Randomization codes for all other SAEs will be provided to MSD GS at end of Study if the Study Drug has been blinded in the Study.
 
(iii) MSD may define certain Non-Serious Events of Interest. If any Non-Serious Events of Interest are defined, Merck will provide such information in writing to Principal Investigator at the time of Protocol approval, execution of this Agreement or anytime thereafter. Reporting of any defined Non-Serious Events of Interest will be handled in the same manner as SAEs unless mutually agreed otherwise in writing by the parties.
 
(iv) All reports of Study Drug exposure during pregnancy or lactation (including a female partner of a male Study subject using the Study Drug), whether associated with an AE or not, must be reported to MSD GS in accordance with the timelines and contact information for an SAE. Principal Investigator shall follow pregnancies to term to obtain the outcome of the pregnancy. The outcome of the pregnancy shall be forwarded to MSD GS.
 
(v) Institution and Principal Investigator shall fully comply with all of their respective reporting obligations to the applicable regulatory authorities with respect to any AE, SAE or SUSAR that arises from the Study.
 
(vi) SAE reports and any other relevant safety information are to be forwarded to MSD GS [contact]

2.10 Itemized Study Budget	Annexed sheet

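### Surgeons' satisfaction has no stated instrument, no rule for turning four area ratings into one endpoint, and a planned test that ignores the surgeon who rates

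*Combined protocol and SAP*

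**What the plan says.** Section 2.1.1: "The secondary endpoint is intraoperative bleeding", followed by surgeons' satisfaction. No instrument is given for the latter.

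Section 2.5, surgeon's evaluation, lists specific complaints, operating time lost to poor relaxation, patient motion, and a surgical rating score. The score "consists of individual 4 parts of critical lymph node dissection areas": station 4sb, station 6, the supraduodenal area and the suprapancreatic area. Each is graded 1 to 5.

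The scale itself refers to treatment. At grades 1 and 2, "Additional neuromuscular blocking agents must be given", and grade 3 speaks of a need for more agent. Item 10 of the anaesthetic protocol gives a rocuronium bolus when the surgeon asks for deeper block, in either arm. No text says whether a rating is made before or after a bolus, or how ratings after a bolus are analysed.

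Section 2.7 compares quantitative variables by Mann-Whitney and Wilcoxon tests and adds: "For all statistical tests, a P value < 0.05 was considered significant". It gives no summary rule for the four ratings, no multiplicity adjustment and no hierarchy. It does plan randomisation stratified by surgeon, but does not carry surgeon into the analysis.

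**The concern.** A named secondary endpoint should yield one pre-specified answer. Here the instrument, the summary (mean, total, worst area or any single area) and the number of tests can all be settled after the data are seen. A satisfaction claim could then rest on the most favourable of four correlated ratings.

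Two further gaps affect the same endpoint. Surgeons probably differ in how they use a subjective scale. A test that ignores surgeon leaves that variation in the error term, although the randomisation was designed to control it. Also, a low rating in one area may lead to a bolus, so that later areas are rated under a deeper block. The plan does not say whether that belongs in the comparison.

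**Working it through.** **The plan's own figure.** The only stated calculation concerns lymph nodes: "Based upon a sample size of n=89 patients per group, this study has 80% power to detect a 6.3 difference between groups", with SD 15. Then n = 2 × [15 × (1.960 + 0.842) / 6.3]² = 88.99, so 89 per group. A one-sided test would need 71, so two-sided 0.05 is implied. 178 × 1.10 = 195.8, so 196. The figure reproduces. No error rate or power is stated for satisfaction.

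**False positives if the four areas are tested separately.** Inputs: four ratings (section 2.5) and 0.05 per test (section 2.7). The correlation ρ between the test statistics is not given and is assumed.
- Independent: 1 − 0.95⁴ = 1 − 0.8145 = 18.5%.
- Equicorrelated: P(max|Zᵢ| > 1.96) with Zᵢ = √ρ·U + √(1−ρ)·Eᵢ, where U and Eᵢ are independent standard normal.

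| ρ | any of four, either direction | any of four, favouring deep block |
|---|---|---|
| 0 | 18.5% | 9.6% |
| 0.5 | 15.6% | 7.8% |
| 0.7 | 13.0% | 6.5% |
| 0.9 | 9.4% | 4.7% |

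The single-test references are 5% and 2.5%. A simulation of 5-level ratings compared by Mann-Whitney, 89 per arm and 4,000 trials per setting, gave 15.7%, 14.7% and 11.4% at latent correlations 0.5, 0.7 and 0.9. The mean of the four, tested once, gave 4.4% to 5.5% across latent correlations 0.3 to 0.9.

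**Ignoring surgeon.** Let s be the share of rating variance due to surgeon, with arms balanced within surgeon and d the standardised difference. Normal approximation, n = 89:
- unstratified power = Φ{[d − 1.96√(2/n)] / √[2(1−s)/n]}
- stratified power = Φ{d / √[2(1−s)/n] − 1.96}

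No effect size is given for the rating, so d = 6.3/15 = 0.42 is borrowed from the primary endpoint; s is assumed. At s = 10%, power goes from 81% unstratified to 84% stratified; at s = 30%, from 84% to 92%. The unstratified test is also conservative here: its true level is 2[1 − Φ(1.96/√(1−s))], that is 3.9% at s = 10% and 1.9% at s = 30%. The false-positive rates in the table would be lower to that extent.

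**Ratings after a bolus.** The documents give no bolus frequency in either arm. Suppose that only moderate-arm patients receive a bolus, that a share f do so before a later rating, and that they then rate like the deep arm. The contrast becomes 0.42(1 − f). For f = 0, 10%, 20%, 30% and 40%, power for that rating at 89 per group is 80.0%, 71.3%, 61.1%, 50.1% and 39.0%. This shows the possible size under one-sided assumptions; it is not an estimate.

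**The case against.** A reader might infer that the plan runs four tests at 0.05 and so carries an 18.5% error rate. The documents do not say so. They never state that satisfaction is the rating score; complaints, lost time and patient motion are also listed. One score made of four parts fits a single total or mean as well as four tests. Independence is also implausible when one surgeon rates one operation, so 18.5% is a ceiling. All of this stands. It changes the defect from wrong testing to an undefined endpoint, and that still leaves the choice open until after the data are seen.

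A reader might also infer that rescue hides the difference between arms. That requires more boluses in the moderate arm, and the documents give no frequencies. Comparing block strategies with rescue included is a legitimate question, and dilution towards no difference is conservative for a superiority claim. This stands too, but the plan does not say that this is the question it asks.

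Finally, this is a secondary endpoint: the lymph-node test and its sample size are untouched. That limits the weight of the point but does not remove it.

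**Conclusion.** The point holds as a gap in definition and analysis. The plan names satisfaction, states no instrument, gives no rule for combining four ratings, and compares without regard to surgeon. If the areas were tested separately, the false-positive chance would be about 9% to 18.5%, depending on an assumed correlation, against 5% for one test. Stratifying by surgeon would gain about 3 points of power at an assumed 10% surgeon share and about 8 points at 30%. The bolus effect can be neither sized nor signed from the documents; it would dilute the contrast if boluses are more common in the moderate arm. This should be corrected before analysis, but it does not threaten the primary conclusion.

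**What to change.** In sections 2.1.1 and 2.7:
- Name the surgical rating score as the measure of surgeons' satisfaction.
- Define one value per patient, the mean of the four area ratings.
- Compare it once at two-sided 0.05 with a surgeon-stratified method in place of the unstratified Mann-Whitney test: a van Elteren test, or a linear model with surgeon as a factor.
- Report the four areas descriptively with confidence intervals.
- State that the main comparison includes ratings made after a bolus, so that it compares block strategies with rescue included.
- Add a sensitivity analysis of the first-rated area, scored before any bolus. Any patient given a bolus before that rating needs a stated rule, because exclusion would select on an event after randomisation.

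On the rating form, record the order of the areas and the time of any bolus relative to each rating. The lowest of the four ratings is not a rescue-proof alternative: ratings of 3, 2, 2, 2 without a bolus could become 3, 5, 5, 5 after one, which raises the minimum from 2 to 3.

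The cost is SAP wording, one stratified analysis and two items on the form. The downside is that no separate significance claim can be made for a single dissection area. If such claims are wanted, four tests at 0.0125 each would hold the error at 4.9% or below. No change to the bolus rule is proposed.

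### Section 2.7 names only an unadjusted rank test for the primary node count and does not say how surgeon or BMI enters it; pre-specified adjustment would add precision at no patient cost

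*Combined protocol and SAP*

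**What the plan says.** Section 2.1 sets the outcome: "The primary endpoint is number of harvested lymph node that is critical point regarding quality of surgery in gastric cancer treatment". Its rationale for studying patients with BMI above 25 is that fat hampers the dissection: "The retrieval of lymph nodes (LNs) is difficult because they are embedded in thick fat tissue".

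Section 2.7 then contains four relevant elements:

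- **Test for measured outcomes.** "Quantitative variables were expressed as means (standard deviation) and were compared by Mann-Whitney and Wilcoxon nonparametric tests". The only other tests named are Pearson and Fisher, for qualitative variables.
- **BMI.** The section anticipates that rising BMI affects surgery and states that "we will process it as continuous variable when we analyze data", with a possible BMI cut-off to follow if the result is significant. It gives no model, outcome or role for BMI.
- **Surgeon.** Randomisation is stratified by surgeon, explicitly to control surgeon effects on the results. No matching term or stratum appears in the analysis.
- **Sample size.** With 89 evaluable in each arm, the plan claims that "this study has 80% power to detect a 6.3 difference between groups in harvested lymph nodes". The variability input is a "between subject standard deviation of change of 15 for harvested lymph node".

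Section 2.5 makes BMI and clinical stage (I or II) eligibility criteria, so both are known before randomisation.

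**The concern.** The plan identifies two pre-randomisation factors that it believes matter, surgeon and BMI, but the one test it names for the primary endpoint can take neither. None of the four named tests accepts a continuous covariate, so the stated intention for BMI cannot be carried out with the methods listed. Someone must choose a model later, possibly with the data in view.

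Two things are at stake. Variation in node count that surgeon and BMI explain stays in the error term, in a design sized at 80% power with nothing to spare. And a chance difference in BMI between the arms passes uncorrected into the estimate. Both can be dealt with using information the trial already holds.

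**Working it through.** **Inputs.** From section 2.7: difference 6.3, SD 15, power 80%, alpha 0.05, 89 per group, 10% loss, total 196. Sidedness is not stated; two-sided is assumed because it reproduces the plan's figure, while one-sided gives 71 per group. Not in the documents: R², the share of node-count variance that the covariates explain. Values of 1% to 15% are assumed.

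**The plan's own figure.** n per group = 2 × (1.960 + 0.842)² × 15² / 6.3² = 88.99, so 89. The total is 178 × 1.10 = 195.8, so 196. Both reproduce.

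**Evaluable patients.** 196 × 0.90 / 2 = 88.2, so 88 per arm.

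**Power with adjustment.** Residual SD = 15 × √(1 − R²); SE = residual SD × √(2/88); power = Φ(6.3/SE − 1.96). The equivalent unadjusted size is 88/(1 − R²).

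| Assumed R² | SE (nodes) | 95% CI half-width | Power | Equivalent n per arm |
|---|---|---|---|---|
| 0 (unadjusted) | 2.26 | 4.43 | 79.6% | 88 |
| 1% | 2.25 | 4.41 | 80.0% | 89 |
| 5% | 2.20 | 4.32 | 81.6% | 93 |
| 10% | 2.14 | 4.20 | 83.6% | 98 |
| 15% | 2.09 | 4.09 | 85.6% | 104 |

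**Surgeon share of R².** Stratification already balances surgeon between arms, so the unadjusted estimate itself varies less; only its standard error is too large. If all of a 10% R² came from surgeon, unadjusted power would be Φ((6.3 − 1.96 × 2.261)/2.145) = Φ(0.871) = 80.8%. The gain to 83.6% would then be 2.8 points rather than 4.0, and the unadjusted test would be conservative.

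**Rank test against adjusted model.** The table uses a test of means, whereas the plan names a rank test. A simulation with normal data, 89 per group and 6,000 runs per setting gave:

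| Assumed R² | Mann-Whitney power | Adjusted regression power |
|---|---|---|
| 0 | 76.8% | 79.2% |
| 5% | 76.8% | 81.1% |
| 10% | 77.2% | 83.5% |

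About 2 points of each gap come from the rank test itself and not from the missing covariate.

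**Chance imbalance in BMI.** With 88 per arm, the between-arm difference in standardised BMI has SD √(2/88) = 0.151. An imbalance of 1.96 SD, reached in about 5% of trials, is 0.295. It moves the node difference by 0.295 × 15 × √R²: 0.4, 1.0 or 1.4 nodes at R² of 1%, 5% or 10%. Against the SE of 2.26 that is 0.20, 0.44 or 0.62 of a standard error.

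**The case against.** The strongest reply is that this is a preference for efficiency whose benefit cannot be measured from the documents. Much of that stands:

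- No R² is given. Every patient has BMI above 25, so its range is truncated and its explanatory power may be small. At R² of 1% the gain is 0.4 points.
- Section 2.1 says that fat makes retrieval difficult and prolongs surgery. It does not say that fewer nodes are harvested.
- The usual standard error already allows for chance imbalance. Leaving out covariates neither biases the randomised comparison nor inflates its type I error.
- Node counts may be skewed. The simulation assumed normality, which favours the linear model.

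Three stronger readings are tempting, and the documents support none of them. A reader might infer that BMI is definitely left out of the primary comparison. Section 2.7 says BMI will be analysed as a continuous variable, so the list of methods is incomplete and the role of BMI is undefined, which is not the same as absent. A reader might infer that clinical stage drives node count because two stages are enrolled. Stage appears only as an eligibility line, and nothing links it to yield. As an illustration, if 20% of patients were stage II and yielded 5 more nodes (both assumed), stage would explain 0.2 × 0.8 × 25/225 = 1.8% of the variance. Finally, a reader might infer that a chance imbalance could invalidate the result; the shifts above are well under one standard error.

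What the reply does not answer is that the plan stratifies on surgeon and intends to use BMI, yet names no primary analysis that can use either.

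**Conclusion.** The point holds as a free improvement in precision, not as an error in the trial's validity. The only analysis named for the primary endpoint is unadjusted, while surgeon and BMI are both treated by the plan as influential and known before randomisation. Surgeon is the better supported of the two, being the stratification factor; BMI follows, with its role to be defined.

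The size is uncertain and may be small: from about 0.4 power points at R² of 1% to about 6 at 15%, and somewhat less where the explained variance comes from the balanced surgeon strata. This rests on the plan's own difference and SD, a two-sided 0.05 test, a normal approximation, 88 evaluable per arm and assumed R² values. Because the fix costs no patients, even the lower end justifies it.

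**What to change.** In section 2.7, name the primary analysis as a linear model of harvested node count on arm, with surgeon (the stratification factor) and continuous BMI as pre-randomisation covariates, using robust standard errors. Report the adjusted mean difference with its 95% CI; this also matches the sample-size calculation, which compares two means. Keep the Mann-Whitney test as a sensitivity analysis.

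Say that BMI enters this model as an adjustment covariate, and keep any search for a BMI cut-off separate and labelled exploratory. Clinical stage (I or II, already recorded at eligibility) may be added as an optional covariate if the sponsor has reason to expect that it predicts node count. Decide this before unblinding. The documents do not give the number of surgeons, so state in advance how surgeons with very few patients will be pooled.

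The cost is a few sentences in the plan and one regression. No new patients, measurements or form fields are needed.

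### Randomisation is stratified by surgeon, but the planned test of harvested lymph nodes ignores surgeon and leaves any gain in precision unused

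*Combined protocol and SAP*

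**What the plan says.** - **Endpoint.** Section 2.1.1: "The primary endpoint is number of harvested lymph node". Section 2.7 adds: "The major objective of this study is to estimate the number dissected lymph nodes".
- **Allocation.** Section 2.7 addresses surgeon differences at randomisation: "factors impacting results, we will perform surgeon stratified randomization". Section 2.5 describes the mechanism only in general terms: "The patients were randomly assigned to two groups using a computer-generated randomization table". No block size or other balancing rule is given.
- **Analysis.** Section 2.7 says that quantitative variables "were compared by Mann-Whitney and Wilcoxon nonparametric tests". No test is labelled primary, so this rule applies to node count by default. The only covariate mentioned is BMI.
- **Other use of surgeon.** Section 2.7 foresees "technical problems being able to distort objective data when interim analysis, we would drop the surgeon out of this study". That is removal of a surgeon, not adjustment.
- **Intervals.** Section 2.7: "Qualitative variables were described by numbers and percentages and 95% confidence intervals". Nothing comparable is said for quantitative variables.
- **Sample size.** Section 2.7 gives 89 per group, 80% power and a difference of 6.3 nodes, with a "between subject standard deviation of change of 15 for harvested lymph node". The source of that SD is left as an unfilled placeholder.

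**The concern.** The planners expect surgeon to influence results and build the allocation around it, but then analyse as if it were not there. An unstratified rank test counts differences between surgeons as noise.

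Two consequences follow. First, if surgeon explains part of the variation in node count, power and precision that the design has already made available are not used. Second, if allocation is balanced within surgeon (by permuted blocks, for example), the arm comparison is less variable than the test assumes, so its true type I error falls below 5%. With simple allocation within surgeon the second effect does not arise.

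Separately, a trial that aims to estimate a quantity should commit to an interval for it, and the plan does so only for qualitative variables.

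**Working it through.** **The plan's own figure.** With SD 15, difference 6.3 and a two-sided 5% level, the standard error at 89 per group is 15 × √(2/89) = 2.25. Power is Φ(6.3/2.25 − 1.96) = 80.0%, so the stated size reproduces. A one-sided test would need 71 per group, so two-sided testing is implied.

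**Assumed inputs.** The documents give no surgeon variance share, number of surgeons, block size or data shape. Section 2.3 gives 9 centres, and 9 is used below as an assumed number of surgeons. The surgeon share of total variance is taken as 0, 0.05, 0.10, 0.20 or 0.30, with total SD held at 15.

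**Normal approximation, exact balance within surgeon.** The within-surgeon SD is 15 × √(1 − share).
- Type I error of the unadjusted test, 2 × [1 − Φ(1.96/√(1 − share))]: 5.0 / 4.4 / 3.9 / 2.8 / 1.9%.
- Power of the unadjusted test: 80 / 81 / 81 / 83 / 84%.
- Power of the adjusted test: 80 / 82 / 84 / 88 / 92%.

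**Simulation of the rank tests.** There were 178 patients and 20,000 runs per setting (Monte Carlo error about 0.15 point for type I error, at most 0.3 for power). The comparator is a linear model of the overall ranks on arm with a random surgeon effect (REML, t reference). Results for 9 equal-volume surgeons and normal data:

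| Surgeon share | 0 | 0.05 | 0.10 | 0.20 | 0.30 |
|---|---|---|---|---|---|
| Blocks of 4: Mann-Whitney type I error, % | 4.8 | 4.4 | 4.0 | 3.1 | 2.2 |
| Blocks of 4: Mann-Whitney power, % | 77.5 | 78.5 | 78.7 | 80.9 | 82.4 |
| Blocks of 4: random-surgeon rank model power, % | 77.8 | 79.9 | 81.3 | 85.9 | 89.6 |
| Unblocked: Mann-Whitney type I error, % | 5.1 | 4.8 | 4.8 | 4.9 | 4.9 |
| Unblocked: Mann-Whitney power, % | 77.6 | 78.0 | 78.2 | 78.1 | 79.1 |
| Unblocked: random-surgeon rank model power, % | 77.7 | 78.8 | 80.5 | 84.2 | 88.5 |

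The settings were then widened to 9, 18 or 30 surgeons, equal or unequal volumes, normal or gamma residuals, and blocked or unblocked allocation (100 settings in all). The power gain ranged as follows:

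| Surgeon share | Gain, percentage points |
|---|---|
| 0 | -0.1 to 0.4 |
| 0.05 | 0.5 to 1.4 |
| 0.10 | 1.2 to 2.9 |
| 0.20 | 3.7 to 6.2 |
| 0.30 | 5.7 to 9.5 |

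The type I error of the random-effect rank model stayed between 4.7% and 5.5%.

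**Width of the interval.** The unadjusted 95% half-width is 1.96 × 2.25 = 4.4 nodes. Adjusted for surgeon (9 surgeons, blocked, simulated) it is 4.4 / 4.3 / 4.2 / 4.0 / 3.7 nodes across the five shares. Coverage of the adjusted interval was 94.5 to 95.4%.

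**If 15 is a within-surgeon SD.** The total SD is then 15/√(1 − share) = 15.0 / 15.4 / 15.8 / 16.8 / 17.9. An unadjusted comparison of means has power Φ(6.3/(SD × √(2/89)) − 1.96) = 80 / 78 / 76 / 71 / 65% unblocked. With exact balance it has 80 / 79 / 77 / 73 / 68%.

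**The case against.** The strongest reply is that nothing is invalid. False positives are not inflated, the SD is described as between-subject, which fits a total SD, and on that reading 89 per group is adequate for the unadjusted test. All of this stands, and it limits the point to efficiency.

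The size of the gain cannot be known from the documents. At a share of 0.05 it is about 1 point. Expecting surgeon effects, as Section 2.7 does, does not show that they are large. This also stands. The conservatism is hypothetical too, because no blocking is stated.

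A stratified analysis can cost power when surgeon does not matter. A van Elteren test had about 75% power against 78% at share 0 with 9 surgeons, and fixed surgeon effects with 30 surgeons and no blocking had 69.6% against 77.2%. That is a reason to choose the random effect, not a reason to leave surgeon out. The simulations assumed additive normal surgeon effects with no surgeon-by-arm interaction, and did not model a surgeon being dropped at the interim analysis.

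Finally, the missing interval and the meaning of the SD are separate matters. An unadjusted interval would fill the first gap, and the text does not rule one out; it only fails to promise one. The second is a question about the source of the SD, and the low powers under the within-surgeon reading should not be charged to the choice of test alone.

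**Conclusion.** The point holds as a matter of efficiency and consistency, for the sponsor to consider. Surgeon defines the randomisation strata and appears in no analysis. Under the assumed shares, adjusting gains about 1 percentage point of power at 0.05 and becomes material only from about 0.10 to 0.20 upward. If surgeon explains no variance, nothing is gained. The planned test keeps its nominal level if allocation is unblocked. If allocation is blocked, its level falls to about 2.2% at a share of 0.30 with 9 surgeons. That the stated power is roughly kept rests on reading 15 as a total SD, which the documents do not confirm.

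**What to change.** Before unblinding, amend the SAP as follows.

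1. Name one primary test of harvested lymph nodes: a linear model of the ranked counts on arm, with surgeon as a random effect.
2. Report beside it the surgeon-adjusted mean difference in nodes with its 95% CI, from the same model on the raw counts. Label this as the estimate and the rank test as the only test, because the two can occasionally disagree.
3. If fixed surgeon effects are preferred, pool low-volume surgeons by centre.
4. State whether allocation is blocked within surgeon.

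**Cost.** Wording only. Surgeon is known for every patient because it is used at randomisation, and no patients are added. With the random effect, the largest power loss in the 100 settings was 0.1 point, within simulation error. With fixed effects and no true surgeon effect, the loss is 0 to 1.7 points if blocked (9 to 30 surgeons), 1 to 2 points with 9 surgeons unblocked, and up to 7.6 points with 30 surgeons unblocked.
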